10.7. Safety Analysis

The safety analyses will be conducted using the Safety Population (all subjects who receive any amount of IP). Adverse events, vital sign measurements, physical examination findings, clinical laboratory test results, injection site assessments, retinal assessment results, ECG interpretations, and concomitant medications and procedures will be tabulated and summarized as appropriate.

Adverse events observed will be classified using the Medical Dictionary for Regulatory Activities (MedDRA) classification system. If clinically significant, any or all laboratory evaluations should be reported as AEs and repeated more frequently, if clinically indicated. The severity of the toxicities will be graded according to the National Cancer Institute (NCI) Common Terminology Criteria for Adverse Events (CTCAE) Version 4.03 whenever possible.

The frequency of AEs will be tabulated by MedDRA system organ class and preferred term. In the by-subject analysis, a subject having the same event more than once will be counted only

once. Adverse events will be summarized by NCI CTCAE grade. Adverse events leading to discontinuation from treatment, events classified as NCI CTCAE Grade 3 or higher, study-drug-related events, and SAEs will be tabulated and listed separately. By-subject listings of all AEs, SAEs, discontinuations due to AEs, and deaths will be provided.

Clinical laboratory data will be summarized. Laboratory data will be graded according to NCI CTCAE Version 4.03 criteria wherever possible. The frequencies of the worst severity grade observed during treatment will be displayed in cross-tabulations by screening status.

Vital signs, ECG, and retinal examination data will be summarized by cross-tabulations presenting normal and abnormal values.

Graphical displays will be provided where useful in the interpretation of results.

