5. TABLE OF EVENTS

Table 1:Table of Events

	Screening Period		Treatment Period								Follow-up Period					
	V1	V2	V3	V4	V5	V6	V7	V8	V9	V10	V11	V12	V13			
	Day -28 to Day 0	Day 1 (±3 days)	Day 15 (±3 days)	Day 29 (±3 days)	Day 57 (±3 days)	Day 93 (±7 days)	Day 120 (±3 days)	Day 155 (±3 days)	Day 186 (±7 days)	Day 246 (±7 days)	Day 306 (±7 days)	Day 365 (±7 days)	Day 425 (±7 days)	Early Termin- ation		
Event		Week 1	Week 2	Month 1	Month 2	Month 3	Month 4	Month 5	Month 6	Month 8	Month 10	Month 12	Month 14			
Informed consent	Х	-	-	-	-	-	-	-	-	-	-	-	-	-		
Inclusion/exclusion criteria	Х	-	-	-	-	-	-	-	-	-	-	-	-	-		
Demography/medical and surgical history including duration of diabetes and diabetic peripheral neuropathy	Х	-	-	-	-	-	-	-	-	-	-	-	-	-		
Prior/concomitant medication and procedures	Х	X	Х	Х	Х	Х	Х	Х	Х	Х	Х	Х	Х	Х		
Physical examination including vital signs (height [at Visit 1 only], weight, body temperature, blood pressure, respiration, and pulse ^a	Х	x	-	х	х	X	Х	х	X	X	х	х	Х	Х		
12-Lead electrocardiogram (ECG) ^f	Х	-	-	-	-	-	-	-	-	-	-	-	-	-		
Clinical laboratory testing (serum biochemistry, hematology, coagulation tests urinalysis). Estimated glomerular (eGFR) filtration rate will be calculated (Screening).	Х	х	-	х	Х	-	-	-	х	-	-	-	Х	Х		
Anti-HLA antibodies	Х	Xe	-	Xe	Xe	Х	-	-	-	-	-	-	-	-		
HbA1c testing	Х	-	-	-	-	Х	-	-	Х	-	-	Х	-	Х		
Obtain blood for exploratory biomarker evaluation prior to administration of IP ^b	X	X	-	X	X	X	-	-	X	-	-	-	-	X		

I able 1: I able of Events (Continue)

	Screening Period	Treatment Period									Follow-up Period						
	V1	V2	V3	V4	V5	V6	V 7	V8	V9	V10	V11	V12	V13				
	Day -28 to Day 0	Day 1 (±3 days) Week	Day 15 (±3 days) Week	Day 29 (±3 days) Month	Day 57 (±3 days) Month	Day 93 (±7 days) Month	Day 120 (±3 days) Month	Day 155 (±3 days) Month	Day 186 (±7 days) Month	Day 246 (±7 days) Month	Day 306 (±7 days) Month	Day 365 (±7 days) Month	Day 425 (±7 days) Month	Early Termin- ation			
Event		1	2	1	2	3	4	5	6	8	10	12	14				
Pregnancy test ^c	Х	Х	-	Х	Х	-	-	-	-	-	-	-	-	Х			
Retinal examination	Х	-	-	-	-	-	-	-	Х	-	-	Х	-	Х			
6 Item Neuropathy Total Symptom Score (NTSS-6)	Х	-	-	Х	-	Х	-	-	Х	-	-	Х	-	Х			
Utah Early Neuropathy Scale (UENS)	Х	-	-	Х	-	Х	-	-	Х	-	-	Х	-	Х			
Neuropathy Impairment Score of the Lower Limb (NIS-LL)	Х	-	-	Х	-	Х	-	-	Х	-	-	Х	-	Х			
Electrophysiologic nerve conduction studies	Х	-	-	-	-	-	-	-	Х	-	-	Х	-	Х			
Hyperspectral imaging	Х	-	-	Х	-	Х	-	-	Х	-	-	Х	-	Х			

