Immunological/Inflammation Assessments

Immunological/inflammation assessment will include the following testing:

• Anti-HLA antibodies as indicated in the Table of Events (Table 1).

Hemoglobin A1c

Hemoglobin A1c will be measured as indicated in the Table of Events (Table 1).

Coagulation Tests

Coagulation tests including assessment of PT/PTT, D-dimers, fibrinogen, and platelets will be assessed as indicated in the Table of Events (Table 1) prior to dosing with IP and approximately 2 hours post-dose. Assessments can be performed within 1 hour of the 2 hour post dose time frame.

Tryptase and Histamine

Tryptase and histamine levels will be assessed on the day of treatment prior to dosing with IP and approximately 2 hours postdose as indicated in the Table of Events (Table 1).

Exploratory Biomarkers

Exploratory biomarkers will be measured as indicated in the Table of Events (Table 1).

Skin Biopsies: Two 3mm thickness skin punch biopsies will be taken at the lateral aspect of the distal legs (2 biopsies; 1 per leg) approximately 10 cm above the lateral malleolus, and two biopsies will be taken at the volar aspect of the forearm (2 biopsies on 1 forearm). Instructions for tissue collection, handling, and shipping instructions are located in the Laboratory Manual.

Contraception: Females of childbearing potential¹ must use adequate contraception for the duration of their participation in the study (which includes 28 days prior to starting IP, during the Treatment Period [including dose interruptions], and during the Follow-up Period). Adequate contraception is defined as the simultaneous use of 2 of the following forms of contraception methods: oral, injectable or implantable hormonal contraception; tubal ligation; intrauterine device (IUD); barrier contraceptive with spermicide; or a vasectomized partner.

Males (including those who have had a vasectomy) must agree to use barrier contraception (latex condoms) when engaging in sexual activity with females of child bearing potential (FCBP) for the duration of their participation in the study, including the Follow-up Period.

Retinal Assessment: Retinal assessment conducted by an ophthalmologist or optometrist will be performed and scored using the International Clinical Diabetic Retinopathy Disease Severity Scale (Appendix B). Results will be recorded in the eCRF and in the source documents.

6-Item Neuropathy Total Symptom Score (NTSS-6): To be completed as outlined in Efficacy Procedures Section 6.4.

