- 17. Estimated glomerular filtration rate (eGFR) < 30 mL/min/1.73 m² at Screening calculated using the Modification of Diet in Renal Disease Study equation (Levey, 2006) or history of an abnormal eGFR < 60 and decline > 15 mL/min/1.73 m² below normal in the past year.
- 18. Bilirubin level > 2 mg/dL (unless subject has known Gilbert's disease) at screening.
- 19. Untreated chronic infection or treatment of any infection with systemic antibiotics within 4 weeks prior to dosing with IP.
- 20. Uncontrolled hypertension (defined as diastolic blood pressure > 100 mmHg or systolic blood pressure > 180 mmHg during screening at 2 independent measurements taken while subject is sitting and resting for at least 5 minutes).

- 21. History of significant cardiac disorders including but not limited to malignant ventricular arrhythmia, CCS Class III-IV angina pectoris, myocardial infarction/ percutaneous coronary intervention (PCI) / coronary artery bypass graft (CABG) in the 6 months prior to signing the informed consent ICF, pending coronary revascularization in the following 3 months, transient ischemic attack/cerebrovascular accident in the 6 months prior to signing the informed consent form, and/or New York Heart Association [NYHA] Stage III or IV congestive heart failure (Appendix C). Note: Stable Canadian Cardiovascular Society (CCS) Class I-II angina is allowed (Appendix D).
- 22. Poorly controlled DM (hemoglobin A1c > 10%) at screening.
- 23. Untreated proliferative retinopathy at screening.
- 24. Life expectancy less than 2 years due to concomitant illnesses.
- 25. History of malignancy within 5 years except for the following circumstances: basal cell or squamous cell carcinoma of the skin, remote history of cancer now considered cured or positive Pap smear with subsequent negative follow-up.
- 26. History of hypersensitivity to any of the components of the product formulation (including bovine or porcine products, dextran 40, and dimethyl sulfoxide [DMSO]).
- 27. Subject has received an investigational agent —an agent or device not approved by the US Food and Drug Administration (FDA) for marketed use in any indication— within 90 days (or 5 half-lives, whichever is longer) prior to treatment with study therapy or planned participation in another therapeutic study prior to the completion of this study or has received previous gene or cell therapy at any time.

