10. STATISTICAL ANALYSES

10.1. Overview

The primary objective of the study is to assess efficacy of PDA-002 in subjects with DPN as measured by the change in epidermal nerve histology at 6 months following IM administration of 2 different doses of PDA-002 or placebo. Assessment of epidermal nerve histology will be quantified using an immunohistochemical technique to determine ENFD.

The secondary objective of the study is to assess the safety and tolerability of IM administration of 2 different doses of PDA-002 or placebo in subjects with DPN. Safety will be assessed by the type, frequency, severity, and potential relationship of adverse events to treatment with IP.

A detailed Statistical Analysis Plan (SAP) will be provided in a separate document. Exploratory biomarker analysis and other experimental evaluations will be outlined in separate documents and will not be included as part of the Clinical Study Report.

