Appendix B:International Clinical Diabetic Retinopathy DiseaseSeverity Scale

International Clinical Diabetic Retinopathy Disease Severity Scale

Proposed Disease Severity Level	Findings Observable upon Dilated Ophthalmoscopy				
No apparent retinopathy	No abnormalities				
Mild nonproliferative diabetic retinopathy	Microaneurysms only				
Moderate nonproliferative diabetic retinopathy	More than just microaneurysms but less than severe NPDR				
Severe nonproliferative diabetic retinopathy	Any of the following:				
	• More than 20 intraretinal hemorrhages in each of four quadrants				
	• Definite venous beading in two or more quadrants				
	• Prominent IRMA in one or more quadrants				
	And no signs of proliferative retinopathy				
Proliferative diabetic retinopathy	One or both of the following:				
	Neovascularization				
	Vitreous/preretinal hemorrhage				

66

IRMA = intraretinal microvascular abnormalities; NPDR = nonproliferative diabetic retinopathy.

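### Section 10.7 names only a normal/abnormal table for a retina graded on five levels, so worsening of existing retinopathy may not be displayed

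*Combined protocol and SAP*

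**What the plan says.** Section 6.1 has an ophthalmologist or optometrist examine the retina, score it on the International Clinical Diabetic Retinopathy Disease Severity Scale and record the result in the eCRF. Appendix B gives that scale five ordered levels: none; mild, moderate and severe nonproliferative; and proliferative. In Table 1 the row "Retinal examination" is marked at Screening, Month 6, Month 12 and Early Termination.

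Section 10.7 mentions retinal data twice. The first mention sets no format: "retinal assessment results, ECG interpretations, and concomitant medications and procedures will be tabulated and summarized as appropriate". The second does: "Vital signs, ECG, and retinal examination data will be summarized by cross-tabulations presenting normal and abnormal values". Neither the section nor Appendix B says which levels count as normal for this table.

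For laboratory data, the same section plans a graded display against baseline: "The frequencies of the worst severity grade observed during treatment will be displayed in cross-tabulations by screening status". Section 10.1 defers detail: "A detailed Statistical Analysis Plan (SAP) will be provided in a separate document". The one exclusion specific to the retina (Section 7.3, criterion 23) is "Untreated proliferative retinopathy at screening".

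**The concern.** A graded safety measurement with a screening baseline is named for a two-category summary. Because only untreated proliferative disease is specifically excluded, subjects with nonproliferative or treated proliferative retinopathy can enrol. If they all count as abnormal at screening, no later deterioration can move them to another cell.

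The retina deserves better resolution in this trial. Section 8.1 describes the product as angiogenic. Section 4.2 says its effect may reach tissue beyond the injected area, and whether the effect is local or systemic is an open question that the study sets out to explore. Appendix B defines the proliferative level by neovascularization or hemorrhage. Safety is the secondary objective. A change of level, above all a change to proliferative disease, is therefore the retinal information a reader would look for, and the named table may not show it.

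**Working it through.** The plan gives no figure to reproduce. The check counts which worsening moves on the five-level scale a two-category table can show.

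**Inputs**
- Five ordered levels (Appendix B): 1 none, 2 mild, 3 moderate, 4 severe nonproliferative, 5 proliferative.
- Two display categories (Section 10.7).
- Eligible screening levels: 1 to 4, and level 5 if treated (Section 7.3, criterion 23), subject to the general exclusions.
- Appendix B gives the finding "No abnormalities" for level 1 only. This supports reading normal as level 1, but the cut is not stated, so all four possible cuts were tried.

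**Counting the moves**
- All worsening moves, from a level to any higher one: C(5,2) = 10.
- Moves starting from existing retinopathy (within levels 2 to 5): C(4,2) = 6.
- Moves from nonproliferative to proliferative (2 to 5, 3 to 5, 4 to 5): 3.

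**Moves hidden by a cut**

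If normal means levels 1 to k, a move is hidden when both ends fall on the same side of the cut. The number hidden is C(k,2) + C(5−k,2):
- k = 1: 0 + 6 = 6
- k = 2: 1 + 3 = 4
- k = 3: 3 + 1 = 4
- k = 4: 6 + 0 = 6

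| Normal means | Hidden, of all 10 | Hidden, of the 6 from existing retinopathy | Hidden, of the 3 to proliferative |
|---|---|---|---|
| none (k = 1) | 6 | 6 | 3 |
| none or mild (k = 2) | 4 | 3 (3–4, 3–5, 4–5) | 2 |
| none to moderate (k = 3) | 4 | 2 (2–3, 4–5) | 1 |
| none to severe (k = 4) | 6 | 3 (2–3, 2–4, 3–4) | 0 |

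On the natural reading (first row), the table shows 10 − 6 = 4 moves, all starting from no retinopathy. No cut hides fewer than 4 of the 10, or fewer than 2 of the 6 from existing retinopathy. The last cut shows every move to proliferative disease but hides all progression short of it. A table on the five levels shows all 10.

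These counts are not weighted by likelihood and are not expected numbers of subjects. A subject already at level 5 cannot worsen in either format.

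**The case against.** **The detail belongs to a SAP that is not in hand.** The Protocol Summary assigns the safety analyses, as well as the efficacy analyses, to a full SAP, and Sections 4.1 and 10.1 also point there. Section 10.7 can be read as an outline: its general clause leaves the form of the retinal tables open, and graphical displays are allowed. The sentence on normal and abnormal values also covers vital signs and ECG, so it may be generic wording. This stands as far as it goes: a graded table is not ruled out. But the protocol does name a format, and nothing in the documents replaces it or commits to the five levels.

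**Worsening would surface elsewhere.** Under Section 11.1, clinically significant worsening of an existing condition is an adverse event, and Section 10.7 lists all adverse events by subject. An important medical event counts as serious, and serious events are followed to the last visit. The unblinded data monitoring committee also sees accumulating safety data. This is a real but partial backstop. It depends on the investigator judging the change clinically significant, and it does not display the grades. The committee's two scheduled reviews are keyed to Month 3, while the first scheduled retinal examination after screening is at Month 6.

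**The counts measure no effect in this trial.** Any two-category summary of five levels loses some moves. With about 8 subjects per arm and no baseline distribution of retinopathy, the number of hidden worsenings cannot be estimated and could be zero. This is correct, and it limits the weight of the point. It does not make the named table suitable.

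**The biological case is selective.** Sections 1 and 4.2 report that in animals the cells were found only at the injection site and draining lymph nodes, and retinal grade is not an endpoint. Both are true. Section 4.2 nevertheless leaves a systemic effect open, and the protocol itself chose to grade the retina.

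**Conclusion.** The concern holds. The only retinal display the protocol commits to has two categories, for a measurement collected on five. If normal means no apparent retinopathy, it hides 6 of 10 possible worsening moves, all 6 from existing retinopathy, and all 3 from nonproliferative to proliferative disease. Under the most favourable cuts it still hides 4 of 10.

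The conclusion rests on two assumptions: that the table has two cells per time point, as the wording suggests, and that the SAP does not already provide a graded table. The first row of figures also depends on the natural reading of normal.

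This should be changed, but its weight is moderate. The grades are recorded and recoverable, and no endpoint, eligibility rule or stopping rule is affected.

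**What to change.** In Section 10.7, and in the SAP, take retinal data out of the normal/abnormal sentence and specify:
- a descriptive table by arm of screening level against Month 6, Month 12 and worst post-baseline level (including Early Termination), on the five Appendix B levels;
- a by-subject listing of grades by visit;
- the rule for combining the two eyes, for example the worse eye, since none is given.

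If the normal/abnormal table is kept alongside, define normal for the retina.

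The cost is one sparse table and one listing, from grades already in the eCRF. At about 8 subjects per arm, the listing will carry most of the information. No testing is involved, and the table is of a kind already planned for laboratory data.

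A separate wording point, given no weight above: Table 1 footnote d and Section 6.3 follow adverse events for 28 days after the last dose, nominally to Day 57 + 28 = Day 85. Sections 6.1 and 11.1 record them throughout the study, and Section 6.3 itself refers to Section 11.1. Both scheduled post-screening retinal examinations (Days 186 and 365) fall after Day 85, so the adverse event backstop for non-serious worsening depends on which window applies. These passages must be reconciled.

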10.8. Interim Analysis

An interim analysis will be conducted when the last subject completed Visit 9 (Month 6).

11. ADVERSE EVENTS

11.1. Monitoring, Recording and Reporting of Adverse Events

An AE is any noxious, unintended, or untoward medical occurrence that may appear or worsen in a subject during the course of a study. It may be a new intercurrent illness, a worsening concomitant illness, an injury, or any concomitant impairment of the subject's health, including laboratory test values (as specified by the criteria in Section 11.3), regardless of etiology. Any worsening (ie, any clinically significant adverse change in the frequency or intensity of a preexisting condition) should be considered an AE. A diagnosis or syndrome should be recorded on the AE page of the eCRF rather than the individual signs or symptoms of the diagnosis or syndrome.

Abuse, withdrawal, sensitivity or toxicity to an investigational product should be reported as an AE. Overdose, accidental or intentional, whether or not it is associated with an AE should be reported on the overdose CRF. See Section 8.2.2 for the definition of overdose. Any sequela of an accidental or intentional overdose of an investigational product should be reported as an AE on the AE eCRF. In previous studies doses that were one half log greater than the highest dose in this study were not associated with any drug related adverse events. If the sequela of an overdose is an SAE, then the sequela must be reported on an SAE report form and on the AE eCRF. The overdose resulting in the SAE should be identified as the cause of the event on the SAE report form and eCRF but should not be reported as an SAE itself.

In the event of overdose, the subject should be monitored as appropriate and should receive supportive measures as necessary. There is no known specific antidote for PDA-002 overdose. Actual treatment should depend on the severity of the clinical situation and the judgment and experience of the treating physician.

All subjects will be monitored for AEs during the study. Assessments may include monitoring of any or all of the following parameters: the subject's clinical symptoms, laboratory, pathological, radiological or surgical findings, physical examination findings, or findings from other tests and/or procedures.

All AEs and SAEs will be recorded by the Investigator from the time the subject signs informed consent until the last study visit and those SAEs made known to the Investigator at any time thereafter that are suspected of being related to IP. AEs and serious adverse events (SAEs) will be recorded on the AE page of the eCRF and in the subject's source documents. All SAEs must be reported to Celgene Drug Safety within 24 hours of the Investigator's knowledge of the event by facsimile, or other appropriate method, using the SAE Report Form, or approved equivalent form.

46

11.2. Evaluation of Adverse Events

A qualified Investigator will evaluate all adverse events as to:

11.2.1. Seriousness

A serious adverse event (SAE) is any AE occurring at any dose that:

- Results in death
- Is life-threatening (ie, in the opinion of the Investigator, the subject is at immediate risk of death from the AE)
- Requires inpatient hospitalization or prolongation of existing hospitalization (hospitalization is defined as an inpatient admission, regardless of length of stay)
- Results in persistent or significant disability/incapacity (a substantial disruption of the subject's ability to conduct normal life functions)
- Is a congenital anomaly/birth defect
- Constitutes an important medical event

Important medical events are defined as those occurrences that may not be immediately life threatening or result in death, hospitalization, or disability, but may jeopardize the subject or require medical or surgical intervention to prevent one of the other outcomes listed above. Medical and scientific judgment should be exercised in deciding whether such an AE should be considered serious.

Any allergic reaction \geq Grade 3 and associated with the IP is to be reported as an SAE.

Events not considered to be SAEs are hospitalizations for:

- A standard procedure for protocol therapy administration. However, hospitalization or prolonged hospitalization for a complication of therapy administration will be reported as an SAE.
- Routine treatment or monitoring of the studied indication not associated with any deterioration in condition.
- A procedure for protocol/disease-related investigations (eg, surgery, scans, endoscopy, sampling for laboratory tests, bone marrow sampling). However, hospitalization or prolonged hospitalization for a complication of such procedures remains a reportable SAE.
- Hospitalization or prolongation of hospitalization for technical, practical, or social reasons, in absence of an AE.
- A procedure that is planned (ie, planned prior to starting of treatment on study); must be documented in the source document and the eCRF. Hospitalization or prolonged hospitalization for a complication remains a reportable SAE.
- Emergency outpatient treatment or observation that does not result in admission, unless fulfilling other seriousness criteria above.

If an AE is considered serious, both the AE page/screen of the eCRF and the SAE Report Form must be completed.

47

For each SAE, the Investigator will provide information on severity, start and stop dates, relationship to IP, action taken regarding IP, and outcome.

